## 1.4 Description of/and Justification for the Route of Administration, Dosage Regimen and Treatment Period(s)

The human complement C5 standing pool is about 200mg in a 70kg individual. Given the molecular weight of C5 (190kDa), the molecular weight of Coversin (16.8kDa) and the fact that it is a 1:1 binding, it would be expected that 1mg of Coversin would bind 11.3mg of C5. However, it has been shown that a 2.26:1 excess of Coversin is necessary to produce optimal binding conditions to C5 [19]. This means that it would take 40.0mg of Coversin to completely neutralise the standing pool of C5 in a 70kg human.

Pharmacokinetic studies in rats have shown that unbound Coversin is rapidly excreted by the renal route and that the serum half-life is ~30minutes whereas Coversin complexed with C5 has a circulating half-life of ~30 hours [6]. The rate of production of C5 by humans is not known precisely. Sissons *et al.* using the Fick Principle and I labelled C5 injected intravenously calculated a daily turnover in normal humans of between 65 and 196µg/kg/24hrs (mean 90µg/kg/24hrs) [20]. It is generally believed that turnover in autoimmune disease is not substantially different to that in normal subjects. On this basis the mean amount of C5 produced daily is 151.2mg and, using the calculation explained above, it would take 30.0mg of Coversin to completely ablate it. These figures indicate that a loading ablation dose for a human is 0.57mg/kg and a maintenance dose is 0.018mg/kg/hr.

#### CONFIDENTIAL

In preclinical models of myasthenia gravis in rats doses of 0.5, 5.0 and 50mg/kg were all found to be significantly more effective than control (vehicle) in mitigating the signs of experimental autoimmune myasthenia gravis (EAMG) in a dose dependent fashion [16]. The Pharmacologically Active Dose (PAD) in laboratory animals (rodents) is therefore estimated at  $\leq 0.5$ mg/kg. In a human *in vitro* model using whole blood from patients with paroxysmal nocturnal haemoglobinuria (PNH), an autoimmune complement dependent condition, it was found that the maximal effect in preventing red cell haemolysis was achieved by a dose equivalent to between 0.3 and 0.7 mg/kg. Above 0.7 mg/kg no additional benefit was seen.

In pharmacokinetic studies in mice it was found that when a single loading dose was administered by the subcutaneous injection route serum complement activity as determined by the CH50 Eq ELISA was totally suppressed and did not return to normal levels until 24 hours later. At 12 hours there was still 45% or more inhibition of terminal complement activity compared to baseline. This level of inhibition was significantly longer than when the drug was administered intravenously and is believed to be because of a reservoir effect combined with relatively slower renal clearance. These observations have yet to be fully confirmed by more extensive metabolic studies but are considered to be a reasonable basis for selecting administration by subcutaneous rather than intravenous injection.

Toxicokinetic samples were taken at intervals following first dose in the cynomolgus monkey repeat dose toxicology study. As the only dose used in this study was 50x the expected human therapeutic dose interpretation must be guarded. Serum complement activity at 15 minutes, 1, 3, 6, 9 and 12 hours was measured using the CH50 ELISA. The results showed that complement activity fell to about 50% of baseline after 15 minutes and to zero at one hour and it remained at that level for the whole of the 12 hour period. Since it is known that any circulating unbound Coversin would have been excreted by the renal route within 2 - 3 hours it may be assumed that the prolonged effect was due to some depot effect associated with the subcutaneous route of administration.

Single and repeat dose toxicology studies in rat and cynomolgus monkey have been performed using doses of up to 200 times (single dose) and 50 times (repeat dose) the expected human dose. In these studies no signs of toxicity were observed, no haematological or biochemical observations fell outside the range of normal and no gross or microscopic signs of pathology were found in any organ or tissue. It has therefore not been possible to set a No Observable Adverse Effect Level (NOAEL) and so a Human Equivalent Dose (HED) has not been established.

In pharmacology studies no toxicity has been observed to date in any species at any dose by any route of administration. These have included up to 50mg/kg intraperitoneally and up to 20mg/kg intravenously and by inhalation. The current

toxicology studies include single and repeat doses of up to 100 fold the likely HED (i.e. 57.0mg/kg in rats and primates).

The Phase I single ascending dose SAD study showed a maximum onset of action between 6 and 12 hours after injection and a slow recovery due to replenishment of C5 by the liver and other tissues so that at 96 hours post-dose CH50 had only returned to about 75% of baseline. This result was unexpected since both onset and duration of action in animals including NHP was substantially faster and it is considered likely that it is due to both a depot effect since humans generally have more subcutaneous adipose tissue than laboratory animals and because the production of C5 by the liver appears to be slower in humans.

The result suggests that, following a single ablating dose of Coversin, it should be possible to dose once a day using a maintenance dose between 25 and 50% of the ablating dose and keep terminal complement activity totally inhibited which is considered necessary in diseases such as PNH. If a fixed dose of 60mg, 50% higher than the 40mg needed to completely ablate C5 in a 70kg individual, is used it should provide adequate initial ablation in all subjects up to 100kg in weight. Similarly a daily maintenance dose of between 25 and 50% of this should be sufficient to provide 24 hour complement inhibition. Paediatric patients and patients of 50kg or less could be treated using a half dose.

In the first patient in the current study however, because the drug supply will be limited for the first 3 - 6 months it is proposed that a dose tailored the patient's actual weight will be used. When lyophilised drug product becomes available and when the supply situation is improved this and other patients may be switched to a fixed dosing regimen.

#### **1.5** Compliance Statement

This Phase II clinical trial will adhere to the trial protocol and will be conducted in compliance with current ICH Good Clinical Practice (GCP) guidelines and all applicable regulatory requirements.

#### **1.6 Description of the Trial Population**

The study population will be minimally 1 patient and maximally 6 patients above the age of 18 with PNH and known resistance to eculizumab. Patients may be male or non-pregnant females using adequate methods of contraception if of childbearing potential.

#### 2.0 TRIAL OBJECTIVE AND PURPOSE

The trial objectives of this study are to demonstrate the safety and efficacy of Coversin when given to patients with PNH and known resistance to eculizumab.

- 1) To assess the safety and tolerability of Coversin at a single ablating dose followed by repeat daily maintenance doses calculated by body weight.
- 2) To assess whether this dosage regimen is sufficient to control the signs and symptoms of PNH (see Endpoints below).

#### 3.0 TRIAL DESIGN

Treatment with Coversin comprises an ablating dose on day 1 and daily maintenance treatment from day 2 onwards. Calculated according to body weight, the ablating dose will be 0.57mg/kg. Thereafter the daily repeat maintenance dose will be titrated according to clinical response and complement inhibition as determined by CH50 ELISA. The initial daily maintenance dose will be 25% of the ablating dose (0.14 mg/kg) and this will be adjusted up or down if necessary once steady state is reached (5 days). This is further explained in chapter 6, TRIAL PROCEDURE .

In order to mitigate the risk of infection by *Neisseria sp* all subjects or patients taking part in the trial will be carefully instructed about precautions to be taken in case of actual or suspected infection. Patients may either be given permanent antibiotic prophylaxis (oral penicillin daily) or be provided with high dose ciprofloxacin and instructed to immediately commence taking it in the event of a suspected infection. In the latter case they will also be told to make immediate contact with the PI or her deputy. In addition all patients will receive immunisation with quadrivalent meningoccal vaccine Anti meningococcal B vaccine has recently been developed and will be given once approved in the country where the patient is treated. Vaccination against meningococci typ ACW135Y is required at the start of the study. Should the first vaccination take place  $\leq 14$  days of commencement of Coversin, then the patient must take high dose antibiotic for the first 2 weeks. This will generally be ciprofloxacin daily (2x 750mg orally, until 2 weeks have elapsed since first vaccination) or alternative antibiotic treatment directed against meningococci.

#### 3.1 Endpoints

Safety:

- Frequency, type and relationship to treatment of AEs and SAEs
- Out of range laboratory parameters (haematology and chemistry)
- Vital signs
- ECG abnormalities Day 0 Day 90

Primary efficacy endpoint:

• Serum lactic dehydrogenase (LDH) AUC from Day 0 to Day 28 compared with 28 days pre-treatment

Secondary efficacy endpoints:

- Haemoglobin at Day 28 and day 90 and Day 180, absolute and change from baseline
- LDH at days 90 and 180
- Haptoglobin at day 28, day 90 and day 180, absolute and change from baseline
- Dependency on blood transfusion
- Quality of Life at days assessed by the FACIT and EORTC QL-C30 instruments compared to Day 0, day 28, 90 and 180

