## **Protocol synopsis**

	Exclusion Criteria:		
	• Pregnancy (females)		
	• Known allergy to ticks or severe reaction to arthropod venom (e.g. bee or wasp venom)		
	• Failure to satisfy the PI of fitness to participate for any other reason		
Treatment Regimen:	Single ablating dose of 0.57mg/kg per subject followed by daily maintenance doses. The initial maintenance dose will be 25% of the ablating dose. If this is insufficient to maintain complement activity at $\leq 10\%$ of baseline (pre-treatment) level after 5 days of treatment the daily maintenance dose will be increased by doubling until that level of inhibition is achieved. In the event of 100% inhibition being achieved the dose may be titrated downwards at the PI's discretion until a satisfactory clinical result is obtained. If at any point in treatment complement activity (CH50) is 50% of baseline or more a further ablating dose of 0.57mg/kg should be given. An increased daily maintenance dose may be required in the event of intercurrent infection or illness. CH50 level should be checked in the event of deteriorating clinical response manifested by rising serum LDH.		
Duration of Treatment:	Patients will undergo an initial period of 6 months treatment according to this protocol. At the expiry of this period, and on the recommendation of the PI, patients will have the option of remaining on long-term Coversin therapy and will enter the long term follow-up study.		
Endpoints:	Efficacy Endpoints:		
	Primary: Reduction in serum LDH from day 0 – Day 28		
	Secondary: Hb, haptoglobin, Fatigue (FACIT), Quality of Life (EORTC QL-C30), PNH RBC clone size, Transfusion requirement		
	Safety Endpoints:		
	Adverse events, ECG, Laboratory results, Vital signs.		
Statistical Methods:	Descriptive statistics		

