#### 6.1 Endpoints

Primary Efficacy Endpoint:

• Significant reduction in mean serum LDH from Day 0 (pre-dose) to Day 28 (AUC)

Secondary Efficacy Endpoints:

- Change in LDH from Day 0 (pre-dose) at monthly intervals after Day 28
- Change in proportion of PNH clone Day 0 Day 90
- Change in mean Hb Day 0 Day 90
- Change in mean Hp Day 0 Day 90
- Change in FACIT score Day 0 day 28- Day 90 Day 180
- Change in EORTC QLQ C30 score Day 0 -Day 28-Day 90 Day 180

Safety Endpoints:

- Frequency, type and relationship to treatment of AEs and SAEs
- Out of range laboratory parameters (haematology and chemistry)
- Vital signs
- ECG abnormalities Day 0 Day 90

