#### **13 STATISTICS**

#### **13.1** Statistical Methods

The statistical approach taken will depend on the number of patients recruited.

If less than 4 patients are recruited, each patient will be analysed separately. Changes in the primary efficacy outcome during the period Day 0 to Day 28 will be analysed using linear regression using all measurements in the analysis. Secondary efficacy outcomes measured multiple times will be analysed in an equivalent manner.

If 4 or more patients are recruited, the patients will be analysed as a single group. Differences between specific timepoints (e.g. Day 0 and Day 28) for the primary and secondary efficacy endpoints will be performed using the paired t-test.

Additionally the change in the primary efficacy outcome over time will also be examined using all measurements. Mixed model will be used to allow for repeat measurements from the same patients, with the patient considered as a random effect.

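### The primary efficacy endpoint is worded three ways, and section 13.1 plans no analysis that is stated to estimate the LDH AUC contrast of section 3.1

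*Combined protocol and SAP*

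**What the plan says.** The primary efficacy endpoint appears in three places.

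- Section 3.1: "Serum lactic dehydrogenase (LDH) AUC from Day 0 to Day 28 compared with 28 days pre-treatment". One 28-day interval is compared with another.
- Section 6.1: "Significant reduction in mean serum LDH from Day 0 (pre-dose) to Day 28 (AUC", where AUC stands in brackets at the end. The reference is Day 0, there is no 28-day pre-treatment period, and a test result is built into the endpoint.
- Synopsis: "Reduction in serum LDH from day 0 – Day 28". The reference is again Day 0, with no AUC and no pre-treatment period. The synopsis methods line reads only "Descriptive statistics".

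Section 13.1 makes the analysis depend on recruitment. "If less than 4 patients are recruited, each patient will be analysed separately", and changes in the primary outcome "during the period Day 0 to Day 28 will be analysed using linear regression using all measurements in the analysis". With 4 or more patients: "Differences between specific timepoints (e.g. Day 0 and Day 28) for the primary and secondary efficacy endpoints will be performed using the paired t-test". It then adds: "Additionally the change in the primary efficacy outcome over time will also be examined using all measurements", by a mixed model with patient as a random effect. Section 13.3 sets p < 0.05 for all comparisons. Section 13.6 limits efficacy data to measurements made while the patient correctly followed the protocol.

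**The concern.** Nothing in section 13 names AUC, says how it would be computed, or refers to LDH before treatment. The endpoint in 3.1 and the analyses in 13.1 are therefore different quantities, and a statistician following 13.1 would not produce the 3.1 result.

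With 1 to 3 patients, which the planned range of 1 to 6 allows, the regression within Day 0-28 is the only planned efficacy analysis. With so few open-label patients, several admissible readings of the primary result leave room to choose among them after the data are seen. The synopsis line on methods also disagrees with the tests planned in 13.1 and 13.3.

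**Working it through.** The documents give no effect size, SD, power or LDH value for this endpoint, so there is no figure to reproduce. The check has two parts.

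**1. Texts side by side**

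| Place | Summary of LDH | Reference |
|---|---|---|
| 3.1 | AUC, Day 0-28 | 28 days pre-treatment |
| 6.1 | mean, with AUC in brackets | Day 0 (pre-dose) |
| Synopsis | reduction, unspecified | Day 0 |
| 13.1, fewer than 4 patients | linear regression within Day 0-28 | none outside Day 0-28 |
| 13.1, 4 or more, t-test | values at specific timepoints | another timepoint, e.g. Day 0 |
| 13.1, 4 or more, mixed model | change over time; how time enters is not stated | none outside Day 0-28 stated |

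No row of 13.1 matches the row for 3.1.

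**2. How far the quantities can differ (illustration)**

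All LDH curves and sampling days below are assumptions. Appendix 1, which holds the sampling schedule, is not in the text available for review. In (a) and (b) AUC is taken against Day 0, because no pre-treatment LDH is given. Regression p-values are from noise-free curves, so they reflect only departure from a straight line.

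(a) *Fall and partial relapse.* LDH falls linearly from 6 to 1.2 xULN by day 5, stays flat to day 21, then regains half of the fall (to 3.6) by day 28.
- AUC = (6 + 1.2)/2 × 5 + 1.2 × 16 + (1.2 + 3.6)/2 × 7 = 18 + 19.2 + 16.8 = 54.
- AUC/28 = 1.93, so the change against Day 0 is 1.93/6 − 1 = −68%.
- Day 28 against Day 0: 3.6/6 − 1 = −40%.
- Regression p: 0.29 with 10 samples (days 0-5, 7, 14, 21, 28), 0.16 with daily samples to day 14 plus days 21 and 28, 0.26 with daily samples throughout, 0.56 with weekly samples.

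(b) *Fast and slow falls.* LDH(t) = 1.2 + 4.8 × 0.5^(t/h), with half-time h in days. The mean over 28 days is 1.2 + 4.8 × h/(28 ln 2) × (1 − 0.5^(28/h)).

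| | h = 1 | h = 4 |
|---|---|---|
| Mean LDH, Day 0-28 (xULN) | 1.447 | 2.182 |
| AUC against Day 0 | −76% | −64% |
| Day 28 against Day 0 | −80.0% | −79.4% |
| Slope per day, 10 samples | −0.090 (p = 0.10) | −0.155 (p = 0.0008) |
| LDH at day 5 (xULN) | 1.35 | 3.22 |

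Day 28 against Day 0 hardly separates the two curves. The slope is steeper for the slower fall, although its AUC is worse.

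(c) *The pre-treatment reference.* Take values of 5, 4.5, 4, 2.5, 1.8, 1.5, 1.5 and 1.5 xULN on days 0, 1, 2, 5, 7, 14, 21 and 28. AUC is 55.6 and Day 28 minus Day 0 is −3.5.
- Pre-treatment mean 3.5 (28-day AUC 98): 55.6/98 − 1 = −43%.
- Pre-treatment mean 5 (140): −60%.
- Pre-treatment mean 6.5 (182): −69.5%.

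The 3.1 result moves with the pre-treatment level. The Day 28 difference and the slope do not.

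**The case against.** The strongest case on the other side is that the consequence is small. Safety is the primary objective, section 13.5 calls this primarily a safety study, and at most 6 patients are treated open label without a comparator group. The e.g. in the t-test sentence also leaves room for a paired test on AUC. Both points stand and limit the weight of the finding. But that room is not a statement that AUC will be tested, and the branch for fewer than 4 patients does not have it.

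A reader might infer more than the documents support:

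- *That 6.1 and the synopsis have no reference at all.* Both refer to Day 0. What they lack is the 28-day pre-treatment period.
- *That slope and AUC contradict each other.* In (a) and (b) every slope is negative and every AUC change is a reduction. Only the ranking of fast and slow falls reverses, and 13.1 plans no such ranking. The 4-day curve also misses the LDH part of the control that section 6.0 expects at day 5 (below 1.5 xULN). On this curve only half-times under 1.25 days meet it, and between 1 and 1.25 days the AUC changes only from −75.9% to −74.8%. Section 6.0 does foresee slower falls, but not as the expected case.
- *That the regression would generally miss a real effect.* It need not. With 10 samples and 10% noise, p < 0.05 occurs in about 0.3% of runs at a 1-day half-time but 99.8% at 2 days. With daily samples to day 14 plus days 21 and 28 it occurs in 94% even at 1 day.
- *That pre-treatment LDH is not collected, or is excluded.* Appendix 1 cannot be read here, and 13.6 is merely silent on it.

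**Conclusion.** The point holds and should be fixed. It rests on the text alone: three wordings of one endpoint, and an analysis section that names neither AUC nor the pre-treatment period. This does not depend on any assumed curve.

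The size is illustrative. One plausible profile gives −68% on AUC and −40% on Day 28 against Day 0, with a non-significant regression in all four sampling schedules. Examples (a) and (b) use Day 0 as reference, so they do not measure the effect of the missing pre-treatment comparator. Example (c) shows only that the 3.1 result depends on it. The consequence for the trial is limited by its size, its open-label design and its primary safety objective.

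**What to change.** Use one primary efficacy definition in the synopsis, 3.1, 6.1 and 13.1. Section 3.1 is the fullest and the natural choice. If the sponsor prefers the Day 0 reference, 3.1 must be changed to match. Under 3.1:

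- Derive each patient's time-weighted mean LDH over Day 0-28 (trapezoidal AUC/28) and over the 28 days pre-treatment, by the same rule.
- State which pre-treatment values qualify. The prohibited-medication list ideally has eculizumab stopped 2 or more weeks before Coversin, with exceptions, so the 28-day window can include values taken during or shortly after eculizumab.
- State how a missing value inside a window is handled. Section 13.4 only says that missing data are not entered.
- With 4 or more patients, use a paired t-test with 95% CI on the two per-patient values. With fewer than 4, report each patient's ratio or difference with the LDH profile.
- Keep the regression, Day 28 against Day 0 and the mixed model as supportive, and say how time enters the model.
- Do not mix references in the main test. Use Day 0 as a sensitivity analysis.
- Say in 13.6 that qualifying pre-treatment LDH is efficacy data, remove the word *significant* from the 6.1 endpoint, and make the synopsis methods line agree with 13.1.

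The cost is wording and one derived variable per window. There are three downsides. The result relies on whatever pre-treatment LDH exists. AUC depends on sampling (for the 1-day half-time, −75.7% with 10 samples and −69.8% with weekly samples, against −75.9% exact). The reported fall will usually be smaller than Day 28 against Day 0 (for the 4-day half-time, −64% instead of −79%).

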#### 4.0 CONTRACEPTION

At this point in time the reproductive safety of Coversin is unknown. Female patients entered into this study should not be pregnant at the time of commencing Coversin therapy and should observe suitable contraceptive methods until such time as reproductive toxicity data become available. Should inadvertent pregnancy occur this should be discussed with the PI in order to decide how to proceed. It is anticipated that reproductive toxicity data will become available by early 2017.

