#### 4.1 Exposure to Partners During the Study

There is a unknown risk of drug exposure through the ejaculate (which also applies to vasectomised males) that might be harmful to the sexual partners, including pregnant partners, of male subjects. Although the risks of this are at present unknown this should be carefully explained to all male patients taking Coversin and they should be advised to use barrier contraception until reproductive toxicity data become available.

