#### 4.2 Sperm Donation

Male subjects should not donate sperm for the duration of the study and for at least 90 days after the last day of Coversin administration.

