#### 9.1 Inclusion Criteria

- Males or females taking adequate contraceptive precautions if of childbearing potential, 18 80 years of age
- Body weight  $\geq$ 50kg and  $\leq$  100kg
- The patient has provided written informed consent.
- Willing to avoid prohibited medications for duration of study (see Exclusion Criteria)
- Must agree to take appropriate prophylactic precautions against Neisseria infection
- Must be counselled regarding the possible reproductive risks of using Coversin and be advised to use an adequate method of contraception pending further data on reproductive toxicology.

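### Contraception ends when reproductive toxicity data arrive, whatever they show, and no minimum period after the last dose is set

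*Combined protocol and SAP*

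**What the plan says.** Five places in the protocol deal with contraception or a related precaution.

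- **Section 4.0 (women).** After saying that reproductive safety is not known, it says female patients "should observe suitable contraceptive methods until such time as reproductive toxicity data become available". It adds: "It is anticipated that reproductive toxicity data will become available by early 2017".
- **Section 4.1 (men).** Exposure through the ejaculate is described as an unknown risk that might harm partners. Male patients should have this explained, and "they should be advised to use barrier contraception until reproductive toxicity data become available".
- **Section 4.2 (sperm donation).** Donation is barred during the study and "for at least 90 days after the last day of Coversin administration".
- **Section 9.1.** The first bullet makes contraceptive precautions a condition of entry. The last bullet says patients must be counselled and "be advised to use an adequate method of contraception pending further data on reproductive toxicology".
- **Section 1.6.** The population is males, or "non-pregnant females using adequate methods of contraception if of childbearing potential".

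On treatment length, the synopsis states: "Patients will undergo an initial period of 6 months treatment according to this protocol". Patients may then move to a separate long-term study.

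**The concern.** The three clauses that say when contraception ends (4.0, 4.1 and the last bullet of 9.1) rest on the existence of data. They do not require anyone to review the data or to find them reassuring. An adverse result would end the written duty just as a clean one would. Nor do they tie contraception to dosing or to the last dose.

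The protocol is also uneven. Under 4.2 a man may not donate sperm until 90 days after his last dose. Under 4.1 the same man could be released from barrier use with a partner while he is still injecting daily.

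Safety is the primary objective of the trial. At stake is a pregnancy, in a patient or a partner, that is exposed to a drug of unknown reproductive risk because the stopping rule was followed as written.

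**Working it through.** The plan gives no figure to reproduce. The check sets the clauses side by side and then asks whether the trigger can fall during or soon after treatment.

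**Comparison of clauses**

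| Clause | Applies to | Stated end | Condition on the findings | Period after last dose |
|---|---|---|---|---|
| 4.0 | Women | Data available | None | None |
| 4.1 | Men, barrier | Data available | None | None |
| 9.1, last bullet | All | Further data | None | None |
| 1.6; 9.1, first bullet | Women in 1.6; both sexes in 9.1 | None stated | Not applicable | None |
| 4.2 | Sperm donation only | End of study plus a period | Not applicable | At least 90 days |

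**Inputs for the dates**

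- Treatment lasts 6 months (synopsis).
- Data are expected by early 2017 (4.0). I assume this means a date D between 1 January and 31 March 2017.
- The post-dose yardstick is 90 days, taken from 4.2 for illustration.
- Start dates are not given. The protocol version is dated 11 November 2015.

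**Cut-offs**

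A patient is still on drug when the data arrive if the start falls after D minus 6 months, and before D.

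- D = 1 January 2017: starts after 1 July 2016.
- D = 31 March 2017: starts after 30 September 2016.

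A patient has less than 90 days of cover after the last dose if the start falls after (D minus 90 days) minus 6 months.

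- D = 1 January 2017: 3 October 2016 minus 6 months, so starts after 3 April 2016.
- D = 31 March 2017: 31 December 2016 minus 6 months, so starts after 30 June 2016.

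**Two illustrative starts**

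| Start | Last dose | Current rule ends, relative to last dose | Last dose + 90 days | That date relative to the current rule |
|---|---|---|---|---|
| 11 November 2015 | 11 May 2016 | 235 to 324 days after | 9 August 2016 | 145 to 234 days earlier |
| 1 December 2016 | 1 June 2017 | 151 to 62 days before | 30 August 2017 | 241 to 152 days later |

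For the early starter the current rule is the more protective one, so replacing it with a bare 90-day rule would be a step back. For the late starter it ends during treatment.

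**Are later starts plausible?** They are plausible but not certain. Section 1.4 refers to dosing the first patient by actual weight "because the drug supply will be limited for the first 3 - 6 months". Section 6.2 sets later patients' fixed maintenance dose from the first patient's results. Section 13.2 allows up to 6 patients, enrolled as they present.

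**The case against.** The strongest reply is that the wording has an obvious sense. Coming straight after the statement that reproductive safety is unknown, waiting for data means waiting until the question is answered. The sponsor may well have intended reassuring data. That stands as a likely intention, but the text does not state it.

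Second, a reader might infer that the protocol requires no contraception at all during treatment. The documents do not support that. Section 1.6 and the first bullet of 9.1 make contraception a condition of the population and of entry, and the natural reading is that it lasts through participation. The investigator may also withdraw a patient in that patient's interest (Sections 5.0 and 7.1), so adverse data need not be ignored. These provisions still give no duration and nothing after the last dose.

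Third, the 90 days is borrowed from sperm donation, and nothing in the documents supports it for women. Section 1.4 gives rat half-lives of about 30 minutes for unbound drug and about 30 hours for drug bound to C5. In the human single-dose study, complement activity was back to about 75% of baseline at 96 hours. These figures do not settle washout in patients, but they leave the right length open, and the April to June 2016 cut-offs depend on the 90 days.

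Fourth, harm needs several things together: a start from about mid-2016, data on time, a literal reading, and a patient or partner who could conceive, among 1 to 6 patients. If the data are late, cover under the current rule lengthens. All of this stands and limits the weight of the point.

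**Conclusion.** The gap in wording is real. The clauses that state when contraception ends do so on the arrival of data, whatever they show, and set no minimum after the last dose. Under the assumed data window and 6 months of treatment, the literal rule could end the duty during dosing for starts after a cut-off between 1 July and 30 September 2016 and before the data arrive. It could end the duty within 90 days of the last dose for starts after a cut-off between 3 April and 30 June 2016.

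A reader might go further and conclude that patients will be released while exposed, or that the current rule is generally too short. Neither follows. Start dates are unknown, and a patient starting at the protocol date would be covered for 235 to 324 days after the last dose.

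Priority is minor to moderate. The point concerns participant safety and does not touch endpoints, analysis or sample size. The consent pages and the long-term follow-up protocol were not available and may contain fuller wording.

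**What to change.** Amend 4.0, 4.1 and the last bullet of 9.1 in the same way:

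1. Require contraception (barrier for men) throughout Coversin treatment and for at least a fixed period after the last dose. Use 90 days to match 4.2, or another period that the sponsor justifies for each sex.
2. State that the arrival of reproductive toxicity data does not by itself end this minimum. Allow earlier release only by protocol amendment, after a documented review finds the data reassuring.
3. For patients already past the minimum, keep the present data condition, but end it at a documented review of the data by the sponsor and investigator, whatever its outcome, with individual advice to the patient.

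The third step matters. If release always required a reassuring result, adverse or equivocal data would bind a patient who had stopped the drug indefinitely.

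The cost is wording in three places, plus the patient information and the long-term protocol if they match; both should be checked. Some late starters would use contraception for longer: 152 to 241 days in the 1 December 2016 example, if the review is complete by 30 August 2017. For the 11 November 2015 example nothing changes if the review coincides with the data; a later review adds the time until it is done. Because every route to release comes after the data are available, nobody is released sooner than under the present text.
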